Study Protocol with Statistical Analysis Plan

Prospective Randomized Study of the modulating effect of MEXIDOL® as an adjuvant stimulant of the cognitive-emotional component of the rehabilitation treatment in patients with acute cerebral failure

NCT Number: NCT06221826

Pharmasoft
April 10, 2023

Study Protocol

The study procedures for the visits are presented in Table 1.

Conditions	Acute Cerebral Failure (Ischemic Stroke, Traumatic Brain Injury)
Study Design	Study Type: Interventional Primary Purpose: Treatment Study Phase: Phase 4 Interventional Study Model: Parallel Assignment Number of Arms: 2 Masking: None (Open Label) Allocation: Randomized (1:1) Enrollment: 60 [Actual] Time Frame: 66 days (I: parenteral therapy 10 days; II: oral therapy 8 weeks)
Arms	Mexidol and Standard Therapy Standard Therapy
Method of Application	Mexidol, solution for intravenous (IV) and intramuscular administration, IV 500 mg for 10 days, then Mexidol FORTE 250, film-coated tablets 250 mg, orally 1 tablet 3 times a day for 8 weeks.
Standard and Concomitant therapy	Standard treatment: basic practices of kinesitherapy, occupational therapy, speech therapy, clinical psychology, supplemented by adjuvant procedures of electrotherapy and rehabilitation environment therapy. The patient's rehabilitation load was at least 3 hours a day for 12 days. Patients may continue their pre-study therapy for other chronic conditions if, in the opinion of the investigator, they do not interfere with the results of this study and are administered at a stable dose during the study.
Primary Purpose	To evaluate the effect of pharmacological modulation of the rehabilitation process with the drug Mexidol as an adjuvant component of rehabilitation treatment of emotional and cognitive disorders in patients with Acute Cerebral Failure (Ischemic Stroke, Traumatic Brain Injury).
Secondary Purpose	To establish the possibility of identifying an individual clinical response to Mexidol therapy (responders and non-responders) and to determine indications for including the drug in an individual rehabilitation program.

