Exploratory Purpose	 To establish, using neurophysiological methods, the effect of the drug on perfusion-metabolic coupling (TCDG-EEG [transcranial dopplerography and electroencephalography] monitoring at the time of drug infusion) as an indirect indicator of increased metabolic activity of the brain. To establish, using clinical scales, the presence of a connection between the use of the drug Mexidol and the dynamics of recovery of the emotional-cognitive status of patients with acute cerebral insufficiency, during the period of permanent inpatient-outpatient rehabilitation treatment.
Research objectives (Outcome Measures)	1. Assessment of attentiveness and performance – the presence of the effect of Mexidol infusion on the change in the results of the Schulte test [work efficiency] before the start of the course, at the end of the

	course of infusion therapy and after the course of therapy with the			
	tablet form of Mexidol FORTE 250			
	Dynamics of cognitive status according to the Montreal Cognitive			
	Assessment (MoCA test)			
	3. Severity of depression according to the Beck Depression Inventory			
	(BDI scale)			
	4. Reduction in anxiety according to the Hospital Anxiety and			
	Depression Scale (HADS)			
	5. The degree of severity and dynamics of the Post Intensive Care			
	Syndrome (PICS) according to the PICS-score			
	6. Dynamics of level of mobility according to the Rivermead index			
	7. Dynamics of the level of life according to the Rehabilitation Routing			
	Scale (RRS)			
	8. Severity and dynamics of muscle strength according to the Muscle			
	Strength Quantitative Rating (MRC) Scale			
	9. Variants of specific dynamics of neurophysiological parameters of			
	perfusion (transcranial dopplerography) and metabolism			
	(electroencephalography) at the time of infusion of Mexidol (event			
	related monitoring)			
Safety and Tolerability	Incidence of Treatment-Emergent Adverse events related to Mexidol			
Criteria:	S			
Inclusion Criteria:	• ≥18 years old			
inclusion Criteria.	Signed Informed Consent Form			
	Acute Cerebral Failure (Ischemic Stroke, Traumatic Brain Injury)			
	 Montreal Cognitive Assessment (MoCA test) >15; ≤22 			
Evaluaion Cuitonio				
Exclusion Criteria:	• < 18 years old			
	• Epilepsy			
	• Pregnancy			
	Acute failure of one or more organ systems			
	 Purulent-inflammatory disease of any localization Participating in any other clinical trial 			

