For statistical analysis of quantitative features, compliance with the normal distribution law will be preliminarily assessed by one of the generally accepted methods (Shapiro-Wilk criterion). When testing statistical hypotheses for indicators with a normal distribution, parametric criteria will be used, and for indicators whose distribution differs from normal, nonparametric criteria will be used.

The following indicators will be calculated as descriptive statistics parameters for continuous (quantitative) data:

- n number of valid observations;
- M, Mean arithmetic mean;
- Me, Median median;
- Min minimum value;
- Max maximum value;
- Q1 lower quartile;
- Q3 upper quartile;
- Range range;
- IQR interquartile range;
- SD standard deviation;
- SE standard error of the mean;
- w Wilcoxon-Mann-Whitney test for independent groups;
- t Student's t-test with Welch's correction for independent groups;
- f Fisher's exact test;
- $\gamma 2$ Chi-square test.

For ordinal, categorical and qualitative variables:

- absolute frequency (number of observations);
- relative frequency (expressed as a percentage).

The results of the assessment of quantitative variables, the distribution of which corresponds to the law of normal distribution, will be presented as M±SD, where M is the mean value, and SD is the standard deviation. The results of the assessment of quantitative variables, the distribution of which does not correspond to the law of normal distribution, will be presented as Me [Q1; Q3], where Me is the median, and Q1 and Q3 are the lower and upper quartiles.

Efficacy and safety indicators, as well as their changes, will be presented using descriptive statistics by visits and therapeutic groups. For study visits, qualitative (dichotomous) indicators will be compared between groups based on the Pearson $\chi 2$ criterion, the Pearson $\chi 2$ criterion with Welch's correction, or the Fisher exact test for tables of arbitrary dimension (if the frequency of the indicator in at least one of the subgroups is 5 or less).

Comparison of groups by quantitative indicators can be carried out using the Student's T-test and the Mann-Whitney test. Comparison of intra-group parameters before and after treatment can be

performed using the T-test for related samples or the Wilcoxon-Mann-Whitney test. Statistically significant values are p-level <0.05.

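### A normality pre-test with no stated unit chooses the efficacy test and the summary, so one scale can be analysed differently from visit to visit; name one baseline-adjusted comparison instead

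*Combined protocol and SAP*

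**What the plan says.** The Statistical Analysis Plan states that, for quantitative variables, "compliance with the normal distribution law will be preliminarily assessed by one of the generally accepted methods (Shapiro-Wilk criterion"). The result selects the test family: "When testing statistical hypotheses for indicators with a normal distribution, parametric criteria will be used", with rank methods for variables that fail the check. The same result selects the summary, mean with SD or median with quartiles.

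The SAP later adds, permissively, "Comparison of groups by quantitative indicators can be carried out using the Student's T-test and the Mann-Whitney test". Within-group comparisons are likewise "performed using the T-test for related samples or the Wilcoxon-Mann-Whitney test". The significance rule is "Statistically significant values are p-level <0.05".

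The SAP does not state:
- whether normality is tested per arm or pooled, at each visit or once, or on scores, changes or residuals;
- the level of the Shapiro-Wilk test;
- which test applies to any named outcome or visit;
- any baseline-adjusted efficacy comparison (repeated-measures ANOVA is named for safety parameters only).

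The entry rule in the protocol synopsis is "Montreal Cognitive Assessment (MoCA test) >15; ≤22". Table 1 repeats MoCA and the Schulte test at Days 10 and 66. It repeats BDI, HADS, Rivermead, MRC, PICS and RRS at Days 10, 38 and 66.

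**The concern.** A t-test compares means. Mann-Whitney compares the ordering of two distributions. If a pre-test at each visit decides which is used, the quantity estimated for one scale can change between Day 10, Day 38 and Day 66, and the data choose it. A reader could then be shown a median and a rank p-value at one visit and a mean and a t-test p-value at the next, with no common effect size to follow over time.

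Because the unit tested is not stated and the later sentence permits both tests, the choice stays open until the data are seen. The trial is open label. The SAP says that analysts will not be managing patients, but not that they will be blinded to arm.

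The rule also takes the place of a better analysis. Comparing follow-up scores by either test ignores the baseline value, which in a trial of 60 patients is the cheapest source of precision available.

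**Working it through.** The plan gives no means, SDs, effect size or power, so there is no figure of its own to reproduce. Every distribution below is an assumption.

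**Inputs from the documents.** "Allocation: Randomized (1:1) Enrollment: 60 [Actual", so 60/2 = 30 per arm. Entry MoCA takes the integers 16 to 22, which is seven values. Alpha is 0.05, assumed here for Shapiro-Wilk too.

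**1. Can one outcome change branch between visits?** If each visit is tested separately and every test has its nominal 5% rejection rate, with independent visits:
- two visits differ with probability 2 × 0.05 × 0.95 = 0.095;
- three visits are not all on one branch with probability 1 − 0.95³ − 0.05³ = 0.1425.

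That is the rate for perfectly normal data. For moderately skewed scores (gamma, shape 4 or 8), simulated Shapiro-Wilk rejection at n = 30 is 0.44 or 0.26 per arm. If failure in either arm triggers the rank branch, q = 1 − (1 − r)²:
- shape 4: q = 1 − 0.56² = 0.69, and switching is 2 × 0.69 × 0.31 = 0.43;
- shape 8: q = 1 − 0.74² = 0.45, and switching is 2 × 0.45 × 0.55 = 0.495.

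These treat visits as independent, which repeated scores on the same patients are not. Simulated with within-patient correlation:

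| Correlation between visits (assumed) | Two visits on different branches |
|---|---|
| 0.5-0.8 | 33-46% |
| 0.85 | 29-32% |

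A separate simulation of MoCA (entry score plus a rounded normal change, capped at 30) puts Day 10 and Day 66 on different branches in 21-46% of trials if tested pooled, and 22-32% if tested per arm.

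**2. What does the MoCA window do?** Shapiro-Wilk rejection of integer entry scores:

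| Entry distribution within 16-22 (assumed) | One arm, n = 30 | Pooled, n = 60 |
|---|---|---|
| Normal, mean 19, SD 2 | 46-47% | 100% |
| Normal, mean 19, SD 3 | 67-68% | 100% |
| Uniform | 88% | 100% |
| Normal, mean 22, SD 3 | 96% | 100% |
| Normal, mean 24, SD 4 | 97% | 100% |

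All ten distributions tried gave 100% when pooled. The coarse scale does much of this: for continuous scores truncated to the same window, pooled rejection is 12% for mean 19, SD 2, and 90% for mean 22, SD 3. At follow-up the window no longer applies. Pooled rejection is then 9-24% at Day 10 and 10-50% at Day 66.

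**3. What happens to type I error?** Following the pre-test strictly gives 4.8-5.3% across normal, gamma and exponential scores. On simulated Day 10 MoCA it gives 4.9-6.2%, where Welch's test alone gives 4.9-6.0%. The standard error of a rate from 3,000 replicates is √(0.05 × 0.95/3000) = 0.4 percentage points, so the two do not differ materially. Taking the smaller of the two p-values gives 5.7-6.9%.

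**4. What does ignoring baseline cost?** Assume a true difference of 0.6 SD and baseline correlation ρ of 0.5-0.7. The MoCA assumptions above imply similar values: ρ is about SD(entry)/√(SD(entry)² + SD(change)²), which is 1.65/√(1.65² + 3²) = 0.48 to 2/√(2² + 2²) = 0.71. ANCOVA divides the SD by 1/√(1 − ρ²), so the standardised effect becomes:
- ρ = 0.5: 0.6/√0.75 = 0.69;
- ρ = 0.7: 0.6/√0.51 = 0.84.

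Simulated power at 30 per arm is 75% and 89%, against 62-63% for the SAP's rule applied to follow-up scores. If the SAP's rule were applied to changes, the standardised effect would be 0.6/√(2(1 − ρ)), which is 0.60 at ρ = 0.5 and 0.77 at ρ = 0.7. ANCOVA is still ahead, but by less at the higher correlation.

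**The case against.** The strongest reply is that the rule does little harm if followed. The SAP says which family will be used according to the distribution, and the later permissive sentence can be read as listing the tests available under that rule. Strict use keeps error near 5%. On simulated MoCA with a 1.5-point difference, power is 51-58% for both the conditional rule and Welch's test and 48-56% for Mann-Whitney. The two tests reach different verdicts in only about 2% of null trials and 4-7% of trials with a true difference. This stands: a reader might infer that the pre-test inflates type I error, and the figures do not show that. The 6-7% needs an analyst to run both tests and keep the smaller p-value.

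A reader might also infer that the MoCA entry window forces MoCA onto rank tests. It does not. The window binds at entry only, and entry scores are not the treatment comparison. At follow-up most simulated trials pass the normality test. If a single pooled entry result did fix the branch for all visits, the test would then not vary by visit, so the two complaints cannot both hold under one reading of the SAP.

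Nor does the SAP say that raw scores are what is tested. It also refers to changes. The supportable criticism is that the unit is unstated.

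Finally, the SAP already lists mean, SD, median and quartiles for continuous data and already names Welch's correction, so part of the remedy is in place. What remains unanswered is that no outcome has a fixed test, the summary presented is data-chosen, and baseline is not used.

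**Conclusion.** The point holds as a failure of pre-specification. A Shapiro-Wilk test with no stated unit or level chooses both the test and the summary, and under moderately skewed scores about 30-45% of visit pairs would land on different branches. Pooled entry MoCA will almost surely fail the test; per arm the chance is 46-97% depending on the assumed distribution. Neither result decides the follow-up comparison.

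The consequences are a quantity that can change between visits, room to choose between two p-values, and power of 62-63% where baseline adjustment would give 75-89% for an assumed 0.6 SD effect. No material loss of type I error control is shown under strict use. The score distributions, correlations and effect size are all assumed, because the documents give none. The change is worth making because it is cheap, not because the stated rule is badly wrong.

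**What to change.** In the SAP:
1. Delete the normality test as a rule for choosing tests or summaries. Residual plots may be kept as diagnostics.
2. For each quantitative outcome at every post-baseline visit, compare arms by ANCOVA adjusted for that outcome's own baseline value, and report the adjusted mean difference with its 95% CI. The entry criterion already requires a MoCA score, and Table 1 marks the Schulte test, BDI, HADS, Rivermead, MRC and PICS at Day 1. State which scales are treated as quantitative, since the SAP summarises ordinal variables separately as frequencies.
3. Run Mann-Whitney on change from baseline, with the Hodges-Lehmann shift, as a labelled sensitivity analysis.
4. Report mean, SD, median and quartiles for every scale at every visit, whatever the distribution.

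The cost is SAP wording and slightly more tabulation, with no new data collection. The downside is that on strongly skewed scales ANCOVA may be slightly less efficient than ranks; the sensitivity analysis would show whether this matters.

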Ethical and Lagal Aspects	This study will be conducted with the highest respect for the individual			
Ethical and Legal Aspects				
	participants in accordance with the requirements of this study protocol			
	and also in accordance with the following:The ethical principles that have their origin in the Declaration of			
	Helsinki.			
	International Conference on Harmonisation E6 Good Clinical			
	Practice: Consolidated Guideline.			
	All applicable laws and regulations, including, without limitation, privacy laws, clinical trial disclosure laws, and regulations.			
	privacy laws, clinical trial disclosure laws, and regulations.			

Table 1. Schedule of study procedures.

	Visit				
	Screening				
The study procedures		Visit 2 Day 1	Visit 3 Day 10	Video visit 4 Day 38	Visit 5 Day 66
Obtaining Informed Consent					
Checking inclusion/exclusion criteria		X			
Collection of anamnesis data					
Conducting a physical examination		X			
Measurement of BMI	X				
Body temperature	X				
Vital signs of the body's condition (mean BP, HR, RR)	X	X	X		X
Randomization		X			
The Rehabilitation Routing Scale (RRS)	X X		X	X	X
The Montreal Cognitive Assessment (MoCA test)			X		X
The Beck Depression Inventory (BDI scale)		X	X	X	X
The Hospital Anxiety and Depression Scale (HADS)		X	X	X	X
The Rivermead index		X	X	X	X
The Muscle Strength Quantitative Rating Scale (MRC)		X	X	X	X
The Post Intensive Care Syndrome (PICS) score		X	X	X	X
The Schulte test		X	X		X
Neurophysiological parameters (EEG, TCDG)		X			
Administration of the study drug intravenously		X	XX		
Dispensation of the study drug for oral administration			X		
Return of the drug and assessment of treatment compliance (if the drug is taken orally)					X
Question about the intake of concomitant drugs		X	X	X	X
Monitoring of adverse events		X	X	X	X

Statistical Analysis Plan

To create conditions for an independent assessment of the obtained results, statistical data processing at the end of the study will be performed by employees not involved in the management of patients participating in the study. Data processing will be performed in the software environment of the TIBCO® StatisticaTM v.13 and R v.4.4.1 and higher packages or similar, corresponding to the tasks of statistical analysis.

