Safety analysis will be performed for the safety population. The following safety parameters are provided for in this study:

- Total number of AEs, stratified by severity and frequency;
- Frequency of AEs, related, in the opinion of the physician-investigator, to the use of the study drug;
- Frequency of serious adverse events (SAEs), related, in the opinion of the physician-investigator, to the use of the study drug;
 - Proportion of patients with at least one AE;
 - Proportion of patients with 2 or more AEs.

The dynamics of quantitative safety parameters relative to baseline values will be assessed and compared with each other using ANOVA with repeated measures. This method allows to simultaneously check for statistically significant dynamics (at least one average value at one time point differs from the others), and also to compare the dynamics and ranges of the indicator values when obtaining the compared drugs. In case of inappropriateness of the use of parametric methods, a similar analysis of the change in the distribution of indicators during therapy will be carried out using non-parametric analogues - the Friedman criterion and the Wilcoxon signed rank criterion, and intergroup comparisons of changes - using the Wilcoxon-Mann-Whitney criterion.

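### The SAP sets no efficacy analysis set or missing-data rule, so Day 66 defaults to patients with a value and can be biased in either direction if loss differs by arm

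*Combined protocol and SAP*

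**What the plan says.** The SAP lists descriptive statistics for continuous data, beginning with "n number of valid observations". It then says that efficacy and safety indicators are summarised by visit and treatment group. Dichotomous indicators are compared at visits by chi-square or Fisher tests. For the scales: "Comparison of groups by quantitative indicators can be carried out using the Student's T-test and the Mann-Whitney test". Within-group change is tested with paired tests.

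The safety part of the SAP opens with "Safety analysis will be performed for the safety population". That population is not defined, and it is the only one named. Repeated-measures ANOVA also appears only there, for quantitative safety parameters. No sentence defines an efficacy set, says that patients are analysed in the arm assigned, or says what happens to missing values, withdrawals or patients who stop the drug.

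The protocol describes a randomised 1:1 trial, "Masking: None (Open Label"), with 60 patients enrolled (marked as actual) and 66 days of follow-up. Table 1 schedules the efficacy scales at Day 66 with no condition that the patient is still on treatment. It also schedules tablet return and a compliance assessment at that visit. MoCA and the Schulte test are done at Days 10 and 66 but not at Day 38.

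**The concern.** The primary purpose, emotional and cognitive recovery, is judged with these by-visit tests. A two-sample or paired test omits anyone without the value it needs. Since no other method is given, following the SAP as written compares those who have a Day 66 value. Randomisation protects that comparison only if the patients missing from each arm are alike in number and prognosis.

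There are reasons to expect that they may not be. Treatment is open label. Only the Mexidol arm has tablets to take at home (3 a day x 7 days x 8 weeks = 168), and only that arm has compliance to assess. Control patients know that they receive no study drug and may leave for that reason. Because compliance is assessed but linked to no analysis set, nothing in the SAP rules out excluding poor compliers from the Mexidol arm after results are seen. The control arm has no matching exclusion.

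Cognition is the most exposed. A patient lost after Day 10 has no MoCA or Schulte value from the whole oral phase.

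**Working it through.** The documents give no dropout rate, SD, effect size or sample-size derivation, so there is no stated figure to reproduce. What follows is a range under stated assumptions.

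**Inputs from the documents.** 60 patients at 1:1, so about 30 per arm; significance at p < 0.05 (taken as two-sided).

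**Assumptions.** No true effect. Leavers would have scored g SD worse than stayers, with the same g in both arms. The share lost is dT on Mexidol and dC on control. The SD is 1 among stayers.

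**Bias.** If an arm's full mean is 0, then (1 - d) x S + d x (S - g) = 0, so the stayers' mean is S = d x g. The available-case difference is therefore g x (dT - dC).

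**False results favouring Mexidol.** With SE = sqrt(1/nT + 1/nC), n = 30 x (1 - d) and Phi the standard normal distribution function, the chance is 1 - Phi(1.96 - bias/SE). Example, 20% vs 5% with g = 1: nT = 24, nC = 28.5, SE = 0.277, bias = 0.15, ratio = 0.541, chance = 7.8%.

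| Loss, Mexidol vs control | g (SD) | Bias (SD) | Normal approximation | Simulated Welch test |
|---|---|---|---|---|
| 15% vs 5% | 0.5 | 0.05 | 3.8% | 3.8% |
| 15% vs 5% | 1.0 | 0.10 | 5.6% | 5.3% |
| 20% vs 5% | 0.5 | 0.075 | 4.6% | 4.6% |
| 20% vs 5% | 1.0 | 0.15 | 7.8% | 7.3% |
| 25% vs 5% | 0.5 | 0.10 | 5.4% | 5.2% |
| 25% vs 5% | 1.0 | 0.20 | 10.6% | 10.1% |

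The simulation used 20,000 trials per row. The nominal figure is 2.5%.

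**Opposite direction.** Swapping the arms reverses the sign. At 5% vs 20% with g = 1 the bias is -0.15 SD. False results favouring Mexidol fall to 0.6%, and those against it rise to 7.8%.

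**Equal loss.** If dT = dC and g is the same, the bias is g x 0 = 0 and the one-sided rate stays at 2.5%, although leavers do worse. The cost is precision. A 20% loss in both arms takes 30 per arm to 24, and the difference detectable with 80% power, (1.96 + 0.84) x sqrt(2/n), goes from 0.72 to 0.81 SD.

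**Does using Day 10 help?** Suppose that loss depends on the Day 10 value, at an assumed 22% vs 7%, with a correlation of 0.7 between Days 10 and 66. In simulation, an available-case bias of 0.11 SD falls to about 0 once Day 10 data are used. If loss depends on the unseen Day 66 value itself, Day 10 data cannot be relied on to remove the bias, hence the sensitivity analysis below.

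**The case against.** Three stronger readings are tempting, and the case against each of them is sound.

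- A reader might infer that patients who stop Mexidol are dropped from Day 66. The documents do not say so. A patient who stops tablets but attends has a value, and an available-case test would count it. As written, the default is a comparison of attendees, not of those who completed treatment. What stands is that inclusion of these patients is left undefined.
- A reader might take the count of valid observations as a rule restricting the tests. It is a reporting item that an all-randomised analysis would also show. The available-case default follows from the choice of tests and the absence of any missing-data method.
- A reader might conclude that the plan favours Mexidol because leavers do worse. That is not sufficient. Loss must also differ between arms, and the documents give no loss by arm. That only one arm can stop tablets does not show which arm will miss Day 66.

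It is also fair that a mixed model is one reasonable method among several. For MoCA and Schulte it has only Day 10 to draw on besides baseline, so it leans on its assumptions. None of this supplies the missing efficacy set or missing-data rule, and no redaction mark in the SAP would explain the gap.

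**Conclusion.** The concern holds as a gap with a conditional consequence. The SAP fixes neither who is in the efficacy analysis nor how missing values are handled, and its tests default to patients with a value at the visit. Under assumed losses of 15-25% vs 5% and a prognostic gap of 0.5-1 SD, the Day 66 difference shifts by about 0.05-0.20 SD. If the Mexidol arm loses more, false results in its favour rise from 2.5% to roughly 4-11%. If control loses more, the shift is the same size against Mexidol. Equal loss of similar patients gives no bias. The size rests entirely on these assumed rates. The direction cannot be known from the documents, and a claim that the plan is tilted towards Mexidol would go beyond them. The bias is modest in most scenarios, but the arms are small and the remedy is cheap, so the change should be made.

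**What to change.** 1. In the SAP, base efficacy on all randomised patients in their assigned arm, whether or not Mexidol was stopped, and state that compliance does not decide inclusion.
2. In the protocol, state that the Table 1 scales are still collected after the drug is stopped, unless the patient withdraws consent to follow-up. As enrolment is reported as actual, this may come too late for some patients; the other items can still be applied to data already collected.
3. Replace the by-visit available-case tests on the scales with a baseline-adjusted mixed model using all post-baseline visits (Days 10 and 66 for MoCA and Schulte). Add one sensitivity analysis that makes the missing values progressively worse in each arm, and report the point at which the conclusion changes. Patients with no post-baseline value do not contribute to such a model, so give their number by arm and include them in the sensitivity analysis.
4. Report last visit and reason for leaving by arm.

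The cost is SAP wording, one protocol sentence and a little more analysis, with no new visits. The model relies on a missing-at-random assumption, which the sensitivity analysis tests. The estimate includes patients who stopped the drug, so it may be slightly smaller than one among completers.

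### No efficacy analysis uses the pre-treatment score, and the between-arm test is not tied to the visit score or the change; the loss is precision and an open analytic choice, not validity.

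*Combined protocol and SAP*

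**What the plan says.** The Statistical Analysis Plan section gives two kinds of test for quantitative indicators.

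- Between arms: "Comparison of groups by quantitative indicators can be carried out using the Student's T-test and the Mann-Whitney test". The SAP's list of statistics describes the t-test as Welch-corrected for independent groups, so it carries no covariate.
- Within arms: "Comparison of intra-group parameters before and after treatment can be" "performed using the T-test for related samples or the Wilcoxon-Mann-Whitney test".

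Both are permissive in wording and share one threshold: "Statistically significant values are p-level <0.05". Changes in efficacy indicators appear only as something to describe: "Efficacy and safety indicators, as well as their changes, will be presented using descriptive statistics by visits and therapeutic groups". A separate list opens "For ordinal, categorical and qualitative variables" and provides frequencies, but the SAP does not say which scales belong there and which count as quantitative.

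The only model in the SAP is in the safety part: "The dynamics of quantitative safety parameters relative to baseline values will be assessed and compared with each other using ANOVA with repeated measures". Its nonparametric fallback includes "intergroup comparisons of changes - using the Wilcoxon-Mann-Whitney criterion".

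Pre-treatment values are available. Table 1 marks Day 1 for BDI, HADS, Rivermead, MRC, PICS and Schulte. The MoCA and RRS rows look displaced by text extraction and are not treated as missing; the MoCA inclusion criterion in any case requires a score at entry.

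**The concern.** Most outcomes are about recovery from a starting level. With about 30 patients per arm, a pre-treatment score that predicts the later score is the cheapest source of precision the trial has, and the efficacy analysis does not use it.

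Two smaller gaps go with this. The SAP does not fix the tested variable, so the visit score or its change could be selected once results are visible. It also does not rank the between-arm test above the within-arm tests. Natural recovery occurs in both arms, and only the between-arm contrast removes it.

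**Working it through.** **Figure in the plan.** The documents give no power, effect size, SD or sample-size derivation, so there is nothing to reproduce.

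**Inputs from the documents.** Enrolment 60 and allocation 1:1 (Study Design row); threshold 0.05 (SAP); MoCA above 15 and up to 22 (Inclusion Criteria).

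**Assumptions, not in the documents.** Exactly 30 per arm, two-sided testing, true effect 0.5 SD, normal scores, equal SDs at both times (set to 1), and a baseline/follow-up correlation rho of 0.3, 0.5 or 0.7.

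**Step 1: power with equal SDs.** The standard error is SD x sqrt(2/30) = SD x 0.258.

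- Raw score: SD 1; noncentrality 0.5/0.258 = 1.94 on 58 df; power 0.478.
- Change: SD sqrt(2(1 - rho)) = 1.18, 1.00, 0.77; noncentrality 1.64, 1.94, 2.50; power 0.363, 0.478, 0.691 (simulated 0.361, 0.479, 0.693).
- ANCOVA: residual SD sqrt(1 - rho^2) = 0.95, 0.87, 0.71; simulated power, 100,000 trials per rho, 0.508, 0.588, 0.753.

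| rho | Raw | Change | ANCOVA | Raw-score n per arm matching ANCOVA |
|---|---|---|---|---|
| 0.3 | 48% | 36% | 51% | 32 |
| 0.5 | 48% | 48% | 59% | 39 |
| 0.7 | 48% | 69% | 75% | 57 |

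At rho 0.5 adjustment is worth 39 - 30 = 9 patients per arm. At rho 0, 0.1 and 0.2 ANCOVA gives 0.472, 0.474 and 0.484 against 0.478 for raw: no real gain, and a loss of less than 1 point at worst.

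**Step 2: MoCA.** The entry window restricts baseline far more than follow-up. Assume a mean of 19, an unrestricted SD of 4, 5 or 6, scores rounded, and only 16-22 kept.

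- An unrestricted rho of 0.5 falls to 0.264, 0.218, 0.186.
- An unrestricted rho of 0.7 falls to 0.420, 0.355, 0.303.
- At SD 5 and unrestricted rho 0.5, the SDs become 1.94 at baseline and 4.44 at follow-up. The SD of the change is then sqrt(1.94^2 + 4.44^2 - 2 x 0.218 x 1.94 x 4.44) = sqrt(19.7) = 4.44, the same as raw. The ANCOVA residual SD is 4.44 x sqrt(1 - 0.218^2) = 4.33.

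Over the six combinations, with an effect of 0.5 follow-up SD and 40,000 trials each, power is 48% for raw, 48-54% for change and 48-55% for ANCOVA. The gain is about 0-7 points over raw and 0-2 over change.

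**Step 3: raw or change chosen afterwards.** Under the null with equal SDs the two test statistics have correlation sqrt((1 - rho)/2) = 0.59, 0.50, 0.39. The chance that at least one is significant is 8.8%, 9.1%, 9.4% (simulated, 200,000 trials: 8.8%, 9.2%, 9.3%). Under the MoCA scenario it is about 6.6-7.8%. These are worst cases, because they assume the smaller p-value is always reported.

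**Step 4: does the safety model fill the gap?** No. The repeated-measures ANOVA and the between-arm comparison of changes stand in one paragraph whose subject is quantitative safety parameters. Baseline as one level of a time factor is also not covariate adjustment.

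**The case against.** The strongest reply is that this is an efficiency choice. The unadjusted randomised test has 5% type I error, and natural recovery does not bias it. The benefit depends on a correlation the documents do not give, and for MoCA it is small. All of that stands.

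The outcome list also points towards change for most scales: Schulte is worded as change, anxiety as reduction, and MoCA, PICS, Rivermead, RRS and MRC wholly or partly as dynamics. Only depression is worded purely as severity. This narrows the raw-or-change gap but does not close it, because outcome wording does not define the tested variable and the SAP mentions changes in efficacy indicators only descriptively.

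Two stronger readings are tempting and are not supported.

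- A reader might infer that chance baseline imbalance invalidates the planned test. At rho 0.7, raw-score type I error is 12.1% in the 33% of null trials with imbalance above 0.25 SD, but 1.5% in the other 67%; 0.333 x 12.1 + 0.667 x 1.5 = 5.0%. This is the precision loss seen another way, not an extra error.
- A reader might infer that a significant within-arm change will be claimed as efficacy. The SAP does not say so, and it names the between-arm comparison first. It does not exclude that use either, so one clarifying sentence is enough.

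Finally, the power figures assume normal scores and do not transfer directly to ordinal or skewed scales.

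**Conclusion.** The point holds as a matter of precision and prespecification. That no efficacy analysis uses the pre-treatment score, and that raw or change is left open, can be read directly from the SAP and is certain. The size is conditional on assumed values. Against the raw score, ANCOVA adds about 3 points of power at rho 0.3, 11 at 0.5 and 27 at 0.7, and nothing at 0.2 or below. For MoCA, under the assumed window scenario, it adds about 0-7 points over raw and 0-2 over change. Leaving the variable open carries a worst-case type I error of about 9%, or 7-8% for MoCA. Nothing here shows that the planned between-arm test is biased or invalid.

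**What to change.** 1. For each efficacy scale, name one visit for the main comparison, for example Day 66, with the other visits supportive.
2. Make the efficacy analysis a between-arm ANCOVA on arm and the scale's own pre-treatment value, and report the adjusted difference with its 95% CI.
3. Name in advance the scales that are ordinal or clearly skewed, and choose one method for them: either rank ANCOVA for the p-value with an unadjusted Hodges-Lehmann difference and CI (rank ANCOVA gives no difference in scale units), or a proportional-odds model with baseline as covariate and an odds ratio.
4. Keep the unadjusted test as a sensitivity analysis on a stated variable, visit score or change.
5. Report within-arm changes descriptively only.

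The cost is SAP wording and one degree of freedom; no new data are needed. The downside is at most about 1 point of power if rho is 0.2 or lower. Enrolment is already listed as an actual 60, so the change must be dated before outcome data are examined. Otherwise the adjusted analysis should be labelled post hoc and shown beside the unadjusted one.
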